		Visit 2 (Office)	Visit 3, 4 & 5 (Phone)	Visit 6 (Phone)	Visit 7 (Phone)	Visit 8 (Office/Virtual Office)	Visit 9 (Office)	Visit 10 & 11 (Phone)	Visit 12, 13 & 14 (Phone)	Visit 15 & 16 (Office/Virtual Office)	Visit 17 (Office/Virtual Office)	Visit 18* (Office)
Visit Window	Enrollment		Day 1, 3 (-1 day), and 5 (-1 day) after Visit 2	Day 7 (-1 day, +2 days) after Visit 2	Day 14 (±2 days) after Visit 2	Day 21 (±3 days) after Visit 2	Day 7 (+7 days) after Visit 8	Day 2 (-1 day) and 4 (-1 day) after Visit 9	Day 7 (±2 days), 14 (±3 days), and 21 (±3 days) after Visit 9	Day 30 (±3 days) and 44 (±3 days) after Visit 9	Day 60 (±7 days) after Visit 9	Day 90 (±7 days) after Visit 9 End of Study
Instruct study subjects that regular weekly uploads of the study pump is required. With Bluetooth connection and the MiniMed Clinical/MiniMed Mobile app, scheduled uploads are not required for subjects with compatible smartphones, as they are designed to occur continuously. Subjects that do not have compatible smartphones will be required to use the Blue Adapter to facilitate uploads to their computers.		X	X	X	X	X	X	X	X	X	X	If applicable
Instruct subjects to give meal bolus of insulin 15-20 minutes before meals during the run-in period and study period		X	X	X	X	X						

*Note: When subjects exit the study early during the study period, all requirements that are listed for Visit 18 apply.
**Note: Office visits should be completed unless there are circumstances that may put patients at risk or where in person visits may not be allowed.

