Companions/care partners will be instructed that they should be with the subject in the same residence or building complex overnight.

If the MiniMed Clinical/MiniMed Mobile app and the Carelink Clinical app are being used, companions/care partners will be instructed that subjects should be connected to CareLink via the appropriate Smartphone app for data uploading and push notifications for low or high blood sugar when they are apart, e.g., at work, other activities. Instructions on the appropriate operation of the apps will be provided.

For study purposes, subjects will be instructed to perform self-monitoring of blood glucose (SMBG) if they are experiencing a severe hypoglycemic event, severe hyperglycemic event, hyperglycemic hyperosmolar syndrome (HHS), or diabetic ketoacidosis (DKA).

Blood ketones will be measured by all subjects using a ketone meter when:

- the subject is symptomatic for high blood glucose or
- the sensor glucose value is >300mg/dL, the BG is checked by fingerstick and, if BG is >300mg/dL, blood ketones should be checked

As a precaution, subjects will be told that they should keep their own insulin pump supplies in a safe place and to have back-up supplies on hand (such as insulin and syringe, or insulin pen) in the event they are asked to revert back to their own therapy during the study or experience study device issues (e.g., infusion set occlusion with high glucose).

Subjects will be instructed to insert study sensors only in the locations that are specified in the User Guide. Subjects should be reminded about appropriate study sensor placement at each office visit. Information about predominant location of study sensor insertions will be collected on an electronic case report form (eCRF) at the end of a subject's participation.

Subjects will be trained on all parts of the device system. Companions/care partners should be trained on how to respond to high or low glucose events. This should involve training conducted by investigational center staff. A training checklist for each subject should be completed by investigational center-based trainers. Companions/care partners should be available for relevant parts or, if desired, all of this training, either in person or virtually.

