9.1 Schedule of Events

Subjects may participate in 2 phases.

Phase 1 (Completed): Subjects participated in a minimum of 18 planned study visits, as presented in **Section 18.4.3**, for approximately 135 days of device wear. Subjects were allowed to enter a continued access period, following the end of the study period. Phase 1 has been completed. For detailed information, see **Section 18.4 Appendix 4: Phase 1**.

Phase 2: Subjects will participate in a minimum of 18 planned study visits, as presented below in **Figure 6**, for approximately 135 days of device wear.

Virtual office visit (audio visual) may be performed for office visits in cases where an office visit is not possible. The exit visit should occur at the office unless an emergent situation occurs.

If the subject visits the investigational center outside of the scheduled study visits, a Visit eCRF will be completed to document the reason for the unscheduled visit.

If subject exits the study early (i.e., before their last scheduled visit), HbA1c requirements that apply to the final visit will be completed for subjects who have completed Visit 9. Refer to CIP341 Questionnaire Guide for collection of early exit survey/questionnaire requirements.

[figure not shown]
The Exit eCRF and all associated activities should be completed for all subjects who have withdrawn, discontinued, or completed the study.

Subjects who transitioned from Phase 1 to Phase 2:

Phase 1 subjects were given the opportunity to transition into Phase 2 upon completion of the Phase 1 study period or at a subsequent continued access period visit. Transitioning subjects were expected to complete all required Visit 1 – Phase 2 activities prior to entering Visit 9 – Phase did not need to complete Visit 2 through Visit 8 of Phase 2.

Refer to **Section 9.1.1, Table 3** for the Visit Details.

Figure 6. Phase 2 Visit Schedule

Note: Phase 1 subjects were given the opportunity to transition into Phase 2 upon completion of Phase 1 – Study Period or at a subsequent continued access period visit. Phase 1 is now complete and the Phase 1 visit schedule is presented in **Section 18.4.2** for reference.

9.1.1 Study Visit Schedule & Scheduled Follow-Up Visit Windows**Visit 1 to Visit 8 should be completed within 45 days.**

- Visit 1 (Office): Consent and screening
 - Collect labs

Run-In Period:

- Visit 2 (Office): Start Run-In
 - Eligibility has been confirmed
 - Start study pump and CGM in Manual Mode

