 - Register and upload study pump in CareLink Personal and CareLink system
 - Ask subjects about adverse events and device performance
- Visit 3 (Phone): Day 1 after Visit 2
 - Ask subjects if they require assistance, e.g., additional training
 - Ask subjects about adverse events and device performance
 - Review CareLink reports
- Visit 4 (Phone): Day 3 (-1 day) after Visit 2
 - Ask subjects if they require assistance, e.g., additional training
 - Ask subjects about adverse events and device performance
 - Review CareLink reports
- Visit 5 (Phone): Day 5 (-1 day) after Visit 2
 - Ask subjects if they require assistance, e.g., additional training
 - Ask subjects about adverse events and device performance
 - Review CareLink reports
- Visit 6 (Phone): Day 7 (-1, +2 days) after Visit 2
 - Ask subjects if they require assistance, e.g., additional training
 - Ask subjects about adverse events and device performance
 - Review CareLink reports
- Visit 7 (Phone): Day 14 (± 2 days) after Visit 2
 - Ask subjects if they required assistance, e.g., additional training
 - Ask subjects about adverse events and device performance
 - Review CareLink reports
- Visit 8 (Office/Virtual Office): Day 21 (± 3 days) after Visit 2
 - Ask subjects about adverse events and device performance
 - Review CareLink reports

Study Period:

- Visit 9 (Office): Start Study Period, Day 7 (+7) after Visit 8

- Ask subjects about adverse events and device performance
 - Review CareLink reports
 - Start subjects on SmartGuard
 - Start auto basal target at 120 mg/dL
- Visit 10 (Phone): Day 2 (-1 day) after Visit 9
 - Adjust pump settings as needed
 - Ask subjects if they require assistance, e.g., additional training
 - Ask subjects about adverse events and device performance
 - Review CareLink reports
- Visit 11 (Phone): Day 4 (-1 day) after Visit 9
 - Adjust pump settings as needed
 - Ask subjects if they require assistance, e.g., additional training
 - Ask subjects about adverse events and device performance
 - Review CareLink reports
- Visit 12 (Phone): Day 7 (± 2 days) after Visit 9
 - Adjust pump settings as needed
 - Ask subjects about adverse events and device performance
 - Review CareLink reports
- Visit 13 (Phone): Day 14 (± 3 days) after Visit 9
 - Adjust pump settings as needed
 - Ask subjects about adverse events and device performance
 - Review CareLink reports
- Visit 14 (Phone): Day 21 (± 3 days) after Visit 9
 - Adjust pump settings as needed

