Train subjects on the use of the 780G BLE 2.0 insulin pump with DS5		X										
Start study subjects on the 780G BLE 2.0 insulin pump system (Manual Mode)		X										
Provide study subjects the Medtronic infusion sets, reservoirs, sensors and transmitter		X				As needed	As needed			As needed	As needed	As needed
Train subjects on the Medtronic infusion sets, reservoirs, sensors and transmitter		X										
Start study subjects on CGM (transmitter and sensor) and accessories		X										
Instruct subjects to place the sensor in a location that is approved for placement per the User guide and study directions, as applicable		X	X	X	X	X	X	X	X	X	X	If applicable
Train study subjects on the 780G BLE 2.0 SmartGuard features.							X					
Instruct subjects on the SmartGuard feature of the pump as well as specific considerations regarding SmartGuard: 
 Ensure that the Auto Correction feature is turned ON and remains ON throughout the course of the study. 							X					
Instruct subjects to switch from pump therapy to manual injections until issue is resolved if:												

CIP341 Clinical Investigation Plan

D00591227

Revision F

Page 55 of 125

Medtronic

	Visit 1 (Office)	Run-In Period					Study Period					
		Visit 2 (Office)	Visit 3, 4 & 5 (Phone)	Visit 6 (Phone)	Visit 7 (Phone)	Visit 8 (Office/Virtual Office)	Visit 9 (Office)	Visit 10 & 11 (Phone)	Visit 12, 13 & 14 (Phone)	Visit 15 & 16 (Office/Virtual Office)	Visit 17 (Office/Virtual Office)	Visit 18* (Office)
Visit Window	Enrollment		Day 1, 3 (-1 day), and 5 (-1 day) after Visit 2	Day 7 (-1 day, +2 days) after Visit 2	Day 14 (±2 days) after Visit 2	Day 21 (±3 days) after Visit 2	Day 7 (+7 days) after Visit 8	Day 2 (-1 day) and 4 (-1 day) after Visit 9	Day 7 (±2 days), 14 (±3 days), and 21 (±3 days) after Visit 9	Day 30 (±3 days) and 44 (±3 days) after Visit 9	Day 60 (±7 days) after Visit 9	Day 90 (±7 days) after Visit 9 End of Study

Hospital admission is needed for any reasonGlucose is persistently elevated (i.e., above 300 mg/dL) and not responding to correction boluses and/or infusion set change(s).There is an occlusion alarm with elevated glucose, where the study subject is not able to address the occlusion by changing the infusion set												
Adjust pump settings		X	As needed	As needed	As needed	As needed	X	As needed	As needed	As needed	As needed	As needed

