Visit Window	Enrollment		Day 1, 3 (-1 day), and 5 (-1 day) after Visit 2	Day 7 (-1 day, +2 days) after Visit 2	Day 14 (±2 days) after Visit 2	Day 21 (±3 days) after Visit 2	Day 7 (+7 days) after Visit 8	Day 2 (-1 day) and 4 (-1 day) after Visit 9	Day 7 (±2 days), 14 (±3 days), and 21 (±3 days) after Visit 9	Day 30 (±3 days) and 44 (±3 days) after Visit 9	Day 60 (±7 days) after Visit 9	Day 90 (±7 days) after Visit 9 End of Study
Ask subjects about device performance issues and if they called the Medtronic 24 -Hour Technical Support (TS) line to report them. Instruct/Remind subjects to contact the Medtronic 24-Hour TS in the event they experience problems with their study devices.		X	X	X	X	X	X	X	X	X	X	X
Ask subjects if they require assistance, e.g., additional training			X	X	X	X		X				
Ask subjects about the use of SGLT inhibitors during the Continued Access Period												
Remind subjects that the use and wear of study devices throughout the study is a requirement		X	X	X	X	X	X	X	X	X	X	If applicable
Instruct/Remind subjects regarding the content of the Home Reference Guide		X										
Instruct subjects on carbohydrate (CHO) counting as needed (Investigator discretion)		X	X	X	X	X	X	X	X	X	X	If applicable
Instruct subjects on diabetes self-management principles including response to glycemic events, e.g., use of oral glucose/glucagon in case of severe hypoglycemia or checking for ketones in case of severe hyperglycemia Note: Companions/care partners should be trained on how to respond to high or low glucose events.		X										
Instruct subjects and companions/care partners that blood ketone testing is required every time BG is greater than 300 mg/dL, as measured by the Accu-Chek Guide Link study meter.		X	X	X	X	X	X	X	X	X	X	If applicable
Instruct subjects to consider avoiding the use of products containing acetaminophen. If medications containing acetaminophen are taken: 
Wait until use of the medication is stopped before using SG to make treatment decisionsUse additional BG meter readings to verify glucose levels		X	X	X	X	X	X	X	X	X	X	If applicable

CIP341 Clinical Investigation Plan

D00591227

Revision F

Page 58 of 125

Medtronic

	Visit 1 (Office)	Run-In Period					Study Period					

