9.4.10 Transition of Subjects on MDI Therapy To/From Pump Therapy

To assist subjects who enter the study on MDI therapy, investigators and their staff will be instructed on best practices regarding the safe transition from MDI therapy to pump use at the start of the study and a safe transition back to MDI therapy at the end of the study.

For subjects transitioning from MDI to Pump:

- Consider reducing MDI total daily dose by 25% to calculate pump total daily dose before calculating pump settings
- Consider instructing subjects not to administer their long-acting insulin dose the night before/morning of the scheduled pump start.
 - If pump therapy is initiated within 24-36 hours of the last long-acting insulin injection (depending on the duration of action of the brand administered), consider setting a temporary basal rate of 0% to run until that time has passed

For subjects transitioning back to MDI therapy after study participation ends:

- Consider recalculating injection doses based on pump settings, or returning to that subject's previous MDI dose schedule and adjust as needed

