
Risks with the use of an insulin infusion pump may include the risk of malfunction of the components of the system (pump, software, infusion set and reservoir) as well as the risk of use error during use of the system. DDs or use errors can result in administration of too much or too little insulin which can lead to the following clinical consequences:
 
 • Hypoglycemia • Hyperglycemia • Diabetic ketoacidosis or HHS • Severe hypoglycemia with or without associated seizure, coma or death • Kinked cannula leading to hyperglycemia • Infusion set disconnection from pump leading to hyperglycemia • Subject removes the reservoir from the pump but forgets to disconnect the infusion set from the body which results in hypoglycemia or severe hypoglycemia • Dislodged cannula leading to hyperglycemia • A pump error may lead to under delivery or over-delivery of insulin • Battery failure – no insulin delivered • Insulin deterioration leading to hyperglycemia • Incomplete priming; fails to prime tubing and/or cannula, leading to hyperglycemia 	
Prevention and mitigation include:
 
 • Follow the provided user guides & instructions for insulin and insulin pump management which includes information on infusion set change. • Train prior to study device use on appropriate device use and diabetes management principles and instruct to call investigator with problems. • Instruct to check their meter glucose if their high or low symptoms do not match their sensor alerts or SG readings in order to make diabetes treatment decisions. • Instruct to check their meter glucose if there are any concerns that the SG value is not accurate. • Instruct to have glucose and glucagon on hand for hypoglycemia. • Instruct to change infusion set if suspected catheter occlusion or administer insulin with syringe for persistent hyperglycemia especially if ketones develop.

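### The rule for switching from pump to injections should be taught when the pump starts (Visit 2), not first at SmartGuard start (Visit 9)

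*Protocol*

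**What the plan says.** In Table 3 (Section 9.1.1), new Phase 2 subjects are trained on the pump and start it at Visit 2: "Start study subjects on the 780G BLE 2.0 insulin pump system (Manual Mode"). SmartGuard training and instruction follow at Visit 9. Directly below the SmartGuard instruction stands the rule "Instruct subjects to switch from pump therapy to manual injections until issue is resolved if", followed by its three triggers. The SmartGuard instruction has one mark, at Visit 9. A page break splits the switch rule, and its continuation carries no marks of its own. The Phase 1 table (Section 18.4.3) has the same text in one unbroken cell with the SmartGuard instruction, and that cell is marked at Visit 9 only.

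The ketone rule in Table 3, "Instruct subjects and companions/care partners that blood ketone testing is required every time BG is greater than 300 mg/dL", is marked at Visit 2 and at every later run-in contact.

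Other text bears on the run-in:

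- Section 5 tells subjects to "have back-up supplies on hand (such as insulin and syringe, or insulin pen").
- Table 4 (Section 10.1) says: "Instruct to change infusion set if suspected catheter occlusion or administer insulin with syringe for persistent hyperglycemia especially if ketones develop".
- Section 9.4.10 has site staff instructed on "best practices regarding the safe transition from MDI therapy to pump use at the start of the study".
- Under Section 9.1, subjects who moved over from Phase 1 "did not need to complete Visit 2 through Visit 8 of Phase 2".

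**The concern.** The three triggers describe failures of insulin delivery, or circumstances in which a pump should come off. They can arise on the first day of pump use, whether or not the algorithm is running. Most subjects spend the run-in in Manual Mode with SmartGuard off. Subjects on multiple daily injections are eligible (Section 8.3), so for some of them the run-in is their first experience of a pump.

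As the table stands, the explicit instruction to leave pump therapy until the problem is resolved is scheduled only after several weeks of the exposure it is meant to protect against. Table 4 itself lists occlusion or site failure leading to ketoacidosis or a hyperosmolar state as a risk of infusion sets in general. At stake is patient safety during the run-in; no statistical quantity is affected.

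**Working it through.** The plan does not state the interval from Visit 2 to Visit 9, so it is built here from the visit windows in Section 9.1.1.

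**Inputs**

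- Pump start for new Phase 2 subjects: Visit 2.
- "Visit 8 (Office/Virtual Office): Day 21 (± 3 days) after Visit 2", so Visit 8 falls between 21 − 3 = 18 and 21 + 3 = 24 days after Visit 2.
- Visit 9: day 7 (+7 days) after Visit 8, so 7 to 14 days later.

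**Interval from pump start to the visit at which the rule is scheduled**

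- Minimum: 18 + 7 = 25 days
- Nominal: 21 + 7 = 28 days
- Maximum: 24 + 14 = 38 days

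**Marks before Visit 9**

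The contacts from pump start are Visits 2, 3, 4, 5, 6, 7 and 8, which makes 7.

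| Table 3 instruction | Marked contacts, Visits 2–8 |
|---|---|
| Switch to injections (trigger at 300 mg/dL, admission, occlusion) | 0 of 7 |
| Ketone testing (same 300 mg/dL level) | 7 of 7 |

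A further contrast is the warning not to rely on SmartGuard to prevent every glucose excursion. It names SmartGuard, yet it is marked at Visit 2. The switch rule does not concern SmartGuard and is not.

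**Cover for each trigger elsewhere in the protocol**

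| Trigger | Cover before Visit 9 |
|---|---|
| Persistent glucose above 300 mg/dL | Table 4 (syringe insulin), Section 5 (back-up supplies), ketone rule |
| Occlusion not cleared by a set change | Table 4 (replace the set, syringe insulin), Section 5 (back-up supplies) |
| Hospital admission for any reason | None; stated only in the two visit tables |

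The cover for the first two triggers is real, but the Table 4 advice is not tied to a visit. It advises a set change or a dose by syringe; it does not say to stop pump therapy until the problem is resolved.

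**After the change**

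With a mark at Visit 2, the 25–38 day gap becomes 0 days.

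**The case against.** **The row is broken in the text available.** The Phase 2 rule shows no mark at any visit after the page break, so its Visit 9 placement is inferred from its position and from the table of a completed phase. That is fair as a caution. But the Phase 1 cell is unbroken and joins the two texts under a single Visit 9 mark, and Table 3 repeats that text and mark across the page break. No reading of either table puts a mark in the run-in.

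**Subjects are already well protected in the run-in.** They are trained before device use, hold back-up insulin, are told to use a syringe for persistent hyperglycemia, check ketones above 300 mg/dL, and are told at every contact to report changes in health to the site. The Home Reference Guide is also covered at Visit 2. All of this stands, and it keeps the point modest. It covers two triggers in substance, but it does not schedule the explicit rule and does not tell subjects to change to injections on admission. Being under hospital care lessens that risk; it does not deliver the instruction.

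**Unseen documents may carry the rule.** The training checklist, user guides and Home Reference Guide are not among the documents and may already include it. If they do, the edit only brings Table 3 into line with them.

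**An amendment is not free.** IRB handling (Section 16.7) and staff training on the current version (Section 7.2), at up to 40 centers, do cost effort. That is a reason to include the edit in the next amendment, not a reason to leave the table as it is.

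The documents give no event rate for these triggers and no count of subjects new to pumps, so the expected clinical benefit cannot be quantified.

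**Conclusion.** The concern holds. The explicit three-trigger rule for leaving pump therapy is scheduled 25 to 38 days (nominal 28) after new Phase 2 subjects start the pump, and is marked at 0 of the 7 contacts before then. The real gap is narrower than the table alone suggests: the glucose and occlusion triggers have substantive cover elsewhere, while the hospital-admission trigger has none in the documents.

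The conclusion rests on reading the split Table 3 row together with the SmartGuard row above it, as the Phase 1 table supports, and on visits falling within their windows. It applies to new Phase 2 subjects only, because transitioned subjects skipped Visits 2 to 8. The change should be made, as a small safety improvement. It does not bear on the validity of the trial's results.

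**What to change.** Give the switch rule its own row in Table 3, separate from the SmartGuard instruction, with a mark at Visit 2. Keep the mark at Visit 9, both as reinforcement and for transitioned Phase 1 subjects who had no Phase 2 run-in. Add one line to the per-subject training checklist unless it already carries the rule. The clinical content of the rule stays as it is.

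The cost is one split row, one added mark and one checklist line, best included in the next amendment. Sites could be told sooner through a Clinical Bulletin, which Section 16.8.1 already provides for. Endpoints, sample size and analysis are unaffected. The benefit goes to new subjects who have not yet passed the run-in; the documents do not say how many remain.
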